Clinical Trial Protocol

Document Number: c02155664-05	
EudraCT No.:	2014-002413-29
BI Trial No.:	1339.1
BI Investigational Product:	BI 655088
Title:	Safety, tolerability, pharmacokinetics and pharmacodynamics of single rising doses of BI 655088 administered by intravenous infusion in healthy male subjects (single-blind, partially randomised within dose groups, placebo-controlled, parallel group design)
Clinical Phase:	I
Trial Clinical Monitor:	
Phone: Fax:

Principal Investigator:	
Phone: Fax:

Status:	Final Protocol (Revised Protocol (based on global amendment 3))
Version and Date:	Version: 4.0 Date: 22 November 2017
Page 1 of 87	
Proprietary confidential information © 2017 Boehringer Ingelheim International GmbH or one or more of its affiliated companies. All rights reserved. This document may not - in full or in part - be passed on, reproduced, published or otherwise used without prior written permission.	

CLINICAL TRIAL PROTOCOL SYNOPSIS

Name of company: Boehringer Ingelheim		Tabulated Trial Protocol	
Name of finished product: Not applicable			
Name of active ingredient: BI 655088			
Protocol date: 03 December 2015	Trial number: 1339.1		Revision date: 22 Nov 2017
Title of trial: Safety, tolerability, pharmacokinetics and pharmacodynamics of single rising doses of BI 655088 administered by intravenous infusion in healthy male subjects (single-blind, partially randomised within dose groups, placebo-controlled, parallel group design)			
Principal Investigator:			
Trial site:			
Clinical phase:	I		
Objectives:	To investigate safety, tolerability, pharmacokinetics and pharmacodynamics following single rising doses of BI 655088 administered as intravenous (IV) infusion		
Methodology:	Single-blind, partially randomised within dose groups, placebo-controlled, parallel-group design		
No. of subjects:			
total entered:	48*		
each treatment:	8 per dose group (6 on active drug and 2 on placebo)		
	* Additional subjects may be entered to allow for testing of additional intermediate doses within the planned dose range on the basis of experience gained during the trial conduct (e.g. safety or preliminary PK/PD data), i.e. the actual number of subjects entered may exceed 48		
Diagnosis:	Not applicable		
Main criteria for inclusion:	Healthy male subjects, age of 18 to 50 years, body mass index (BMI) of 18.5 to 29.9 kg/m ²		
Test product:	BI 655088		
dose:			
mode of admin.:	IV infusion for 120 minutes		
Comparator product:	Matching placebo (buffer solution)		
dose:	Not applicable		
mode of admin.:	IV infusion for 120 minutes		
Duration of treatment: Single dose			

Name of company: Boehringer Ingelheim		Tabulated Trial Protocol	
Name of finished product: Not applicable			
Name of active ingredient: BI 655088			
Protocol date: 03 December 2015	Trial number: 1339.1		Revision date: 22 Nov 2017
Criteria for pharmacokinetics:	Secondary endpoints: C_{max} , AUC_{0-tz} , and $AUC_{0-\infty}$		
Criteria for pharmacodynamics:			
Criteria for safety:	
Primary endpoint to assess safety and tolerability of BI 655088 is the number [N (%)] of subjects with drug-related adverse events (AEs).
 
Further criteria of interest: AEs including clinically relevant findings from the physical examination, safety laboratory tests, 12-lead electrocardiogram (ECG), continuous ECG monitoring, vital signs (blood pressure [BP], pulse rate [PR], oral body temperature), oral glucose tolerance test (oGTT), bleeding time, anti-drug antibodies (ADA).
		
Statistical methods:	Descriptive statistics will be calculated for all endpoints.		

TABLE OF CONTENTS

TITLE PAGE	1
CLINICAL TRIAL PROTOCOL SYNOPSIS	2
FLOW CHART	4
TABLE OF CONTENTS	6
ABBREVIATIONS	11
1. INTRODUCTION.....	14
1.2 DRUG PROFILE	14
1.2.4 Clinical experience in humans	21
2. RATIONALE, OBJECTIVES, AND BENEFIT - RISK ASSESSMENT	24
2.1 RATIONALE FOR PERFORMING THE TRIAL	24
2.1.1 Starting dose	25
2.1.2 Maximum dose and dose escalation	26
2.2 TRIAL OBJECTIVES.....	26
2.3 BENEFIT - RISK ASSESSMENT	27
3. DESCRIPTION OF DESIGN AND TRIAL POPULATION.....	31
3.1 OVERALL TRIAL DESIGN AND PLAN	31
3.1.1 Administrative structure of the trial	32
3.2 DISCUSSION OF TRIAL DESIGN, INCLUDING THE CHOICE OF CONTROL GROUP	33
3.3 SELECTION OF TRIAL POPULATION	34

3.3.1	Main diagnosis for study entry	34
3.3.2	Inclusion criteria	34
3.3.3	Exclusion criteria	34
3.3.4	Removal of subjects from therapy or assessments.....	36
3.3.4.1	Removal of individual subjects.....	36
3.3.4.2	Discontinuation of the trial by the sponsor	36
3.3.5	Replacement of subjects	37
4.	TREATMENTS.....	38
4.1	TREATMENTS TO BE ADMINISTERED	38
4.1.1	Identity of BI investigational product and comparator product.....	38
4.1.2	Method of assigning subjects to treatment groups	39
4.1.3	Selection of doses in the trial.....	39
4.1.4	Drug assignment and administration of doses for each subject	39

7.5	RANDOMISATION	69
7.6	DETERMINATION OF SAMPLE SIZE	69
8.	INFORMED CONSENT, DATA PROTECTION, TRIAL RECORDS	70
8.1	STUDY APPROVAL, SUBJECT INFORMATION, AND INFORMED CONSENT	70
8.2	DATA QUALITY ASSURANCE	70
8.3	RECORDS	71
8.3.1	Source documents	71
8.3.2	Direct access to source data and documents.....	71
8.4	LISTEDNESS AND EXPEDITED REPORTING OF ADVERSE EVENTS.....	71
8.4.1	Listedness.....	71
8.4.2	Expedited reporting to health authorities and IECs/IRBs.....	71
8.5	STATEMENT OF CONFIDENTIALITY.....	72
8.6	COMPLETION OF TRIAL.....	72
9.	REFERENCES.....	73
9.1	PUBLISHED REFERENCES.....	73
9.2	UNPUBLISHED REFERENCES.....	75
10.	APPENDICES	76
10.1	RECONSTITUTION OF IMP AND INSTRUCTION FOR USE	76
10.1.1	Equipment and material for reconstitution and administration.....	77
10.1.2	Preparation of trial product including placebo for IV infusion	78

11. DESCRIPTION OF GLOBAL AMENDMENT(S)..... 84

ABBREVIATIONS

AE	Adverse event
AESI	Adverse events of special interest
ANOVA	Analysis of variance
ApoE	Apolipoprotein E
AUC _{0-∞}	Area under the concentration-time curve of the analyte in plasma over the time interval from 0 extrapolated to infinity
AUC _{0-tz}	Area under the concentration-time curve of the analyte in plasma over the time interval from 0 to the last quantifiable data point
β	Slope parameter associated with the power model used to evaluate dose proportionality
BA	Bioavailability
BI	Boehringer Ingelheim
BLQ	Below limit of quantification
BMI	Body mass index (weight divided by height squared)
BP	Blood pressure
BSA	Bovine serum albumin
CA	Competent authority
CI	Confidence interval
C _{max(ss)}	Maximum measured concentration of the analyte in plasma (at steady state)
CRF	Case report form
CTP	Clinical trial protocol
CTR	Clinical trial report
CV	Coefficient of variation
DILI	Drug induced liver impairment
DP	Drug product
ECG	Electrocardiogram
EDTA	Ethylenediaminetetraacetic acid
(e)GFR	(Estimated) glomerular filtration rate
ELISA	Enzyme linked immunosorbent assay
HR	Heart rate
IB	Investigator's brochure
IC ₅₀	Half-maximal inhibitory concentration

IEC	Independent Ethics Committee
IRB	Institutional Review Board
ISF	Investigator site file
IV	Intravenous
Ki	Inhibition constant
KI	Knock-in
LC-MS/MS	Liquid chromatography tandem mass spectrometry
MedDRA	Medical Dictionary for Regulatory Activities
MoE	Multinle of exnosure
NC	Not calculated
NK	Natural killer
NOA	Not analysed
NOAEL	No observed adverse effect level
NOP	No peak detectable
NOR	No valid result
NOS	No sample available
NSTEMI	Non-ST segment elevation myocardial infarction
oGTT	Oral glucose tolerance test
PD	Pharmacodynamic(s)
PE	Polyethylene
PK	Pharmacokinetic(s)
PKS	Pharmacokinetic set
PP	Polypropylene
PR	Pulse rate
QT	Time between start of the Q-wave and the end of the T-wave in an electrocardiogram
QTc	QT interval corrected for heart rate using the method of Fridericia (QTcF) or Bazett (QTcB)
R	Reference product or treatment
REP	Residual effect period
SAE	Serious adverse event
SC	Subcutaneous
SCR	Screening
SRD	Single-rising dose
ss	(at) steady state
SUSAR	Suspected Unexpected Serious Adverse Reaction
T	Test product or treatment
TE	Thromboembolism
TGF	Transforming growth factor
t _{1/2}	Terminal half-life of the analyte in plasma

TDMAP	Trial Data Management and Analysis Plan
TMF	Trial master file
TS	Treated set
TSAP	Trial statistical analysis plan
UACR	Urinary albumin / creatinine ratio
ULN	Upper limit of normal

2. RATIONALE, OBJECTIVES, AND BENEFIT - RISK ASSESSMENT

2.1 RATIONALE FOR PERFORMING THE TRIAL

As a transition from preclinical investigations to clinical development in this first-in-man trial, safety, tolerability, pharmacokinetics and pharmacodynamics of BI 655088 will be assessed in healthy male volunteers using single rising intravenous doses in order to provide the basis for a potential ongoing clinical development of BI 655088 in the indication of

The administration of the study drug as IV infusion is considered advantageous since the administration of BI 655088 can be immediately stopped in case safety concerns arise during the running infusion. A further advantage of the IV route is the possibility to investigate suprathreshold exposure unbiased from individual variability in bioavailability. The study will be conducted in healthy volunteers, since healthy volunteers provide a relatively stable physiological, biochemical and hormonal basis for studying drug effects, without an impact by underlying disease or concomitant medication. Healthy volunteers are easy to recruit, easy to select for age and sex, and can be tested under standardized conditions. Therefore, the study population of the planned SRD trial will consist of healthy male subjects aged 18 - 50 years.

Within each dose group, all actively treated individuals will receive the same BI 655088 dose. The next higher dose will only be administered to the next group if the treatment in the preceding dose group was safe and well tolerated (see [Section 3.1](#)). The background for dose selection and escalation steps is described below.

Based on EMA's Guideline on strategies to identify and mitigate risks for first-in-human clinical trials with investigational medicinal products ([R09-6036](#)), BI 655088 can be regarded as a risk compound for the first-in-man trial. EMA identifies 3 main criteria for risk assessment:

- the mode of action
- the nature of the target
- the relevance of animal models

Although BI 655088 is not considered as being a risk compound, a conservative approach in calculating the starting dose has been chosen and safety of participants will be enhanced by appropriate safety measures in the first-in-man trial.

2.1.1 Starting dose

Using the criteria that are described in the EMA Guideline on Strategies to Identify and Mitigate Risks for First-in-Human Clinical Trials with Investigational Medicinal Products ([R09-6036](#)) it would be justified to use a NOAEL approach to select the Maximum Recommended Starting Dose (MRSD) for the first application in humans.

A very similar safe starting dose was defined by PK/PD modeling.

For the first in human trial, g has been chosen as the starting dose. Taken all data together, is expected to be safe and well tolerated.

2.1.2 Maximum dose and dose escalation

Following the initial dose of _____, it is planned to continue the trial with intravenous doses of _____. Dose escalation will not exceed factor 3 and from _____ onwards factor 2. This escalation approach is considered to be safe in the clinical setting where only one single dose will be administered. The selected doses are expected to cover the range of subtherapeutic, lowest to highest anticipated therapeutic as well as suprathreshold doses (for corresponding exposure values, see [Table 2.1.2: 1](#)). The IV doses will be administered by infusion over 120 minutes.

2.2 TRIAL OBJECTIVES

The primary objective of this trial is to investigate the safety and tolerability of BI 655088 in healthy male subjects following intravenous infusion of single rising doses.

Secondary objective is the exploration of the pharmacokinetics and pharmacodynamics of BI 655088 after single dosing.

A description of the endpoints to be determined, and the observations along with specific information as how to collect the data for that information, is provided in [Section 5](#).

2.3 BENEFIT - RISK ASSESSMENT

Participation in this study is without any (therapeutic) benefit for healthy subjects. Their participation in the study, however, is of major importance to the development of a new treatment modality to the current insufficient therapeutic armamentarium of . The subjects are exposed to the risks of the study procedures and the risks related to the exposure to the trial medication.

Procedure-related risks

The use of an indwelling venous catheter for the purpose of blood sampling and on the contralateral arm for the administration of study drug may be accompanied by mild bruising and also, in rare cases, by transient inflammation of the wall of the vein. In addition, in rare cases a nerve might be injured while inserting the venous catheter, potentially resulting in paresthesia, reduced sensibility, and/or pain for an indefinite period. The same risks apply to venipuncture for blood sampling.

The total volume of blood drawn during the entire study per subject might slightly exceed the volume of a normal blood donation (500 mL). No health-related risk to healthy subjects is expected from this blood withdrawal considering that this amount is taken over a period of 3 months.

Drug-related risks and safety measures

Although rare, a potential for drug-induced liver injury is under constant surveillance by sponsors and regulators. Therefore, this study requires timely detection, evaluation, and follow-up of alterations in selected liver laboratory parameters to ensure subjects' safety.

The following safety measures will be applied in this study in order to minimize the risks for trial participants:

- Careful dose selection as described in [Section 2.1.1](#) and [2.1.2](#) with large safety margins up to the maximum dose, and based on a sound preclinical data package including 6 week repeat dose toxicity studies.
- The use of the IV administration has been included in this trial because IV infusions can be stopped should any safety concern arise during administration. The dose will be infused slowly over a period of 2 hours.
- For safety reasons, each dose group is divided into 3 cohorts. On the first study day of each dose level, only 2 subjects (first cohort) will be treated: one will receive active treatment, the other subject will receive placebo. If BI 655088 treatment is safe and tolerated in this first cohort, the following 2 subjects on active will be treated in the second cohort. The second subject on active will be treated at least 2 days after the administration of the first subject. The remaining 4 subjects (either active or placebo) are the third cohort and will be treated no sooner than 2 days following the 2nd cohort. A time interval of at least 10 min will be maintained between each administration of the study drug (start of infusion) to the individual subjects of the 2nd and 3rd cohort. This design ensures that between first and second active dose of each dose level there is a time interval of at least 2 days, which is expected to be sufficient to cover the period of highest risk/peak effect.
- Dose escalation will be shallow. In addition, a time interval of at least 21 days will be maintained between first administration of study drug in the actual dose level and first administration in the next dose level, which is expected to cover the period of highest risk / peak effect. The decision to proceed to the next dose will be based upon the safety and tolerability of the preceding dose. The next dose will only be given if no safety concerns arise in the previous dose group (i.e. no dose-limiting events occur) and if none of the pre-specified trial-specific stopping criteria are met ([Section 3.3.4](#)).
- Doses will only be escalated if previously approved by the principal investigator (or an authorised deputy) and the trial clinical monitor (or an authorised deputy) during its regular Safety Review meetings that will take place prior to each dose escalation (see [Section 3.1](#)).

- Extensive monitoring of ECG and vital signs is incorporated, with continuous ECG monitoring over 4 hours post infusion start to cover the anticipated period of highest drug exposure and additional repeated single 12-lead ECGs following drug administration.
- Extensive safety laboratory testing, determination of bleeding time, and oral glucose tolerance testing will be performed.
- The subjects will stay at the clinical site for at least 48 hours following study drug administration at each dose level. During in-house-confinement the subjects will be under close medical observation and thoroughly monitored for both expected and unexpected adverse events.
- Measurement of BI 655088 plasma concentrations and preliminary determination of pharmacokinetic parameters will be done as described in [Section 7.3.4](#). For precautionary reasons, in a first place maximum drug plasma concentrations of _____ and drug exposure levels _____, respectively, will be considered as a preliminary threshold (see [Section 2.1.1](#)). Further dose progression would only be allowed after a safety interim analysis and filing and approval of a pertinent protocol amendment.

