3. DESCRIPTION OF DESIGN AND TRIAL POPULATION

3.1 OVERALL TRIAL DESIGN AND PLAN

This single-rising dose trial is designed as single-blind, partially randomised, and placebo-controlled within parallel dose groups. “Partially” means that randomisation is done only in the second half of subjects of each dose level. For safety reasons the first half of subjects within each dose group will be administered study drug in a fixed sequence which is unknown to the volunteers: first subject active, second placebo, third active, fourth active.

A total of 48 healthy male subjects is planned to participate in the trial, according to 6 sequential groups comprising 8 subjects per group. However, additional subjects may be entered to allow testing of intermediate doses within the planned dose range on the basis of experience gained during trial conduct (e.g. preliminary PK data), i.e. the actual number of subjects entered may exceed 48. Such changes may be implemented via non-substantial CTP Amendments.

Within each dose group, 6 subjects will receive the active drug and 2 will receive placebo. Only one dose is tested within each dose group. Each dose group will consist of 3 cohorts which will be treated subsequently for safety reasons (see also [Section 2.3](#)).

The dose groups to be evaluated are outlined in [Table 3.1: 1](#) below.

Table 3.1: 1 Dose groups

Dose Group	1	2	3	4	5	6
Dose (mg)						
Number of subjects	8	8	8	8	8	8
Subjects receiving placebo	2	2	2	2	2	2
Subjects receiving active drug	6	6	6	6	6	6
Subject numbers						
Replacement numbers						

The dose groups will be investigated consecutively in ascending order of doses, maintaining a time interval of at least 21 days between the first drug administration in the previous dose group and treatment of a subject in the subsequent dose group. The decision to proceed to the next dose group will be based upon the safety and tolerability data of the preceding dose groups. The next dose will only be given if, in the opinion of the investigator, no safety concerns arose in the preceding dose group (i.e. no dose-limiting events occurred) and if none of the pre-specified trial-specific stopping criteria were met (refer to [Section 3.3.4.2](#)).

A documented Safety Review must take place prior to each dose escalation, but not earlier than 7 days after administration of last subject of a given dose level. Furthermore, an unscheduled safety review meeting can be requested anytime for any reasonable cause by the

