3.3.4.2 Discontinuation of the trial by the sponsor

Boehringer Ingelheim reserves the right to discontinue the trial overall or at a particular trial site at any time for any of the following reasons:

1. New toxicological or clinical findings or serious adverse events invalidating the earlier positive benefit-risk-assessment. More specifically, the trial will be terminated if more

than 50% of the subjects show drug-related and clinically relevant adverse events of moderate or severe intensity, or if at least one drug-related serious adverse event is reported that is considered to be unacceptable.

2. The expected enrolment goals overall or at a particular trial site are not met
3. Violation of GCP, or the CTP, or the contract with BI by a trial site or investigator, disturbing the appropriate conduct of the trial
4. The sponsor decides to discontinue the further development of the investigational product.
5. Dose escalation will be stopped as soon as at least 2 subjects at one dose level on active drug showed relevant individual QT prolongation, i.e. a QTc increase of greater 60 ms from baseline in connection with absolute QT or QTc greater than 500 ms, which has been confirmed by a repeat ECG recording.
6. Dose escalation will be stopped based on the preliminary PK results as per [Section 7.3.4](#),

The investigator / the trial site will be reimbursed for reasonable expenses incurred in case of trial termination (except in case of the third reason).

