5.2.4 Electrocardiogram

5.2.4.1 12-lead resting ECG

Twelve-lead resting ECGs (I, II, III, aVR, aVL, aVF, V1 - V6) will be recorded using a computerised electrocardiograph (Cardionics SA, Brussels, Belgium) at the time points given in the [Flow Chart](#).

In order to achieve a stable heart rate at rest and to assure high quality recordings at comparable resting phases, all ECGs will be recorded for 10-sec duration after the subjects have rested for at least 5 min in a supine position. The site personnel will be instructed to assure a relaxed and quiet environment so that all subjects are at complete rest during the recordings. ECG assessment will always precede all other study procedures of the same time point (except blood drawing from an intravenous cannula which is already in place) to avoid impact of sampling on the ECG quality.

Electrode placement will be performed according to the method of Wilson, Goldberger and Einthoven. Precise electrode placement will be marked with an indelible mark on the skin to allow reproducible placement on day 1 and 2.

Triple ECGs (recorded within 180 sec) will be recorded at screening, as the baseline before drug administration and up to 30 hours after start of infusion. At all other time points single ECGs will be recorded.

All locally printed ECGs will be evaluated by the investigator or a designee.

ECGs may be repeated for quality reasons (like alternating current artefacts, muscle movements, electrode dislocation). For time points with triple ECGs, all three single ECGs will be repeated. For the repeats due to quality reasons, only the repeated ECG recordings will be used for analysis provided quality was better than with the initial ECG.

Additional (unscheduled) ECGs may be collected by the investigator for safety reasons. These ECGs are assigned to the prior scheduled time point. Unscheduled ECGs will not be included into the statistical analysis of interval lengths (if analysis is done).

For the inclusion or exclusion (see [Section 3.3](#)) of a subject and for the assessment of cardiac safety during the study, the QT and QTcB values generated by the ECG machines or their manual corrections by the investigators will be used. In doubtful cases, ECGs may be sent upfront for external evaluation. In this case, these externally measured results would overrule any other results obtained.

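### Meeting the QT stopping criterion before cohort 3 stops escalation by rule, but leaves to discretion whether the last 3 active and 1 placebo subjects at that level are still dosed

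*Protocol*

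**What the plan says.** All references are to the protocol.

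- **Staging (2.3, 3.1, 7.5).** Each dose group has 8 subjects, 6 active and 2 placebo, in three cohorts. The first four follow a fixed sequence: active, placebo, active, active. The last four are randomised.
- **Cohort 1 to cohort 2 (2.3).** This step carries a safety condition: "If BI 655088 treatment is safe and tolerated in this first cohort".
- **Cohort 2 to cohort 3 (2.3).** This step carries only a time condition: "The remaining 4 subjects (either active or placebo) are the third cohort and will be treated no sooner than 2 days following the 2nd cohort".
- **Where the stopping criteria apply.** In 2.3 the next dose is given only "if none of the pre-specified trial-specific stopping criteria are met"; 3.1 says the same. Neither section attaches the criteria to the next cohort at the same dose.
- **QT criterion (3.3.4.2, item 5).** "Dose escalation will be stopped as soon as at least 2 subjects at one dose level on active drug showed relevant individual QT prolongation". A case is a QTc rise of more than 60 ms from baseline with absolute QT or QTc above 500 ms, confirmed on a repeat ECG.
- **Lead-in to that list (3.3.4.2).** The sponsor "reserves the right to discontinue the trial overall or at a particular trial site at any time" for any listed reason, which is permissive.
- **Scheduled Safety Review (3.1).** It precedes each escalation, "but not earlier than 7 days after administration of last subject of a given dose level", and needs safety data from at least 6 subjects of the current group who have completed Day 8.

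**The concern.** The QT criterion is counted within a dose level and takes effect as soon as the second case appears. Enough active subjects are dosed before cohort 3 for it to be met at that point. Its stated consequence protects the next dose group only.

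At stake is whether 3 more healthy volunteers receive an active dose that has already met the trial's own QT stop. This is a first-in-man trial without therapeutic benefit to participants, and the cohorts are staged for safety. A hold in that situation would be expected as a rule rather than a choice.

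**Working it through.** **Counts.** The plan's total reproduces: 6 groups × 8 = 48, that is 36 active and 12 placebo. Within a group, cohorts 1 and 2 hold 1 + 2 = 3 active and 1 placebo. Cohort 3 therefore holds 6 − 3 = 3 active and 2 − 1 = 1 placebo. Since item 5 needs 2 active cases, it can be met before cohort 3.

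**Could a scheduled step intervene?** At the minimum intervals, counting days from the level's first dose as Day 1:

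- cohort 2 on Day 3 and cohort 3 on Day 5;
- Safety Review no earlier than Day 5 + 7 = Day 12;
- next dose group no earlier than Day 1 + 21 = Day 22.

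The review needs data from 6 subjects and only 4 are dosed before cohort 3, so it cannot act as the check.

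**Could item 1 of 3.3.4.2 compel a stop?** It terminates the trial if more "than 50% of the subjects show drug-related and clinically relevant adverse events of moderate or severe intensity". The denominator is not stated. With exactly 2 qualifying cases before cohort 3 at level k:

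- active subjects at the level: 2/3 = 67%;
- all treated at the level: 2/4 = 50%, which is not more than 50%;
- all treated in the trial: 2/(8(k − 1) + 4), so 2/4 = 50% at level 1, 2/12 = 17% at level 2 and 2/44 = 4.5% at level 6.

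Item 1 is exceeded only on the first count, and only if both events are judged drug-related, clinically relevant and at least moderate. Its other limb is an unacceptable drug-related SAE. Meeting item 5 does not in itself trigger either limb.

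**How likely is it?** The documents give no QT event rate, so p is an assumed per-subject rate, independent between subjects.

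- *Cohort 1 condition acts:* a case in the first active subject halts dosing before cohort 2. What remains is a clean first subject and both cohort 2 subjects affected: p²(1 − p).
- *Cohort 1 condition does not act:* any 2 or 3 of the 3 active subjects, 3p²(1 − p) + p³. This is an upper bound.

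| Assumed p | Condition acts | Upper bound |
|---|---|---|
| 2% | 0.0004 × 0.98 = 0.04% | 0.00118 + 0.00001 = 0.1% |
| 5% | 0.0025 × 0.95 = 0.24% | 0.00713 + 0.00013 = 0.7% |
| 10% | 0.01 × 0.90 = 0.9% | 0.027 + 0.001 = 2.8% |
| 20% | 0.04 × 0.80 = 3.2% | 0.096 + 0.008 = 10.4% |

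The upper bound is roughly three times the other figure. It is relevant if, for example, the first subject's QT change appears only after the 2-day interval.

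**Would a check before cohort 3 be feasible?** Triple ECGs are recorded "as the baseline before drug administration and up to 30 hours after start of infusion" (5.2.4.1). That ends 48 − 30 = 18 h before the minimum interval expires.

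**The case against.** The strongest case against is that discretion is well supported here. Item 5 is itself one of the listed grounds on which the sponsor may discontinue the trial. The investigator knows each subject's treatment (4.1.5.2), subjects stay in house for at least 48 h, and cases must be counted in real time because item 5 acts at once. An unscheduled review can be requested at any time (3.1), and urgent safety measures are foreseen (section 8). The cohort 1 condition removes most paths to the problem, and exclusion criterion 20 keeps out subjects with QTc repeatedly above 450 ms. In practice staff would be expected to hold.

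Most of this stands, and it makes the point minor. It does not close the gap, because none of these routes obliges a hold of cohort 3.

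A reader might go further and infer that the protocol directs cohort 3 to be dosed after a QT stop, or that the sentinel design fails. The text supports neither. The cohort 3 interval is a minimum and does not bar a hold, and the stated sentinel aim, at least 2 days between the first and second active dose, is met. Nor should the upper-bound figures be read as the risk, since they assume that the cohort 1 condition never acts.

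One caution applies to the finding itself. The flow chart and parts of the text are not available, so the absence of a mandatory hold is established only for the visible text. Item 5 reads as complete.

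**Conclusion.** The point holds in a narrow form, with minor severity. If item 5 is met before cohort 3, the rule stops escalation but does not require the remaining 3 active and 1 placebo subjects at that level to be held.

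The main residual path has probability 0.04% to 3.2% per level at assumed rates of 2% to 20%; the upper bound, if the cohort 1 condition does not act, is 0.1% to 10.4%. These figures rest on assumed rates and on independence between subjects. The event is improbable unless the dose truly prolongs QT, which is the situation the criterion exists for.

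The protocol states nothing false or contradictory here. The weakness is that a criterion counted within a level has a mandatory consequence only for the next level.

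**What to change.** 1. In 3.3.4.2, item 5, state that dose escalation and further dosing at that dose level will be stopped. This clause creates the rule.
2. In 2.3, state that cohort 3 is dosed only if no stopping criterion has been met at that level.

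Thresholds, sample size and minimum intervals stay as they are. The cost is a protocol amendment, which under 8.1 needs ethics committee and competent authority approval. Cohort 3 may also be delayed briefly when a doubtful ECG is sent for external reading, because that result overrules the local one (5.2.4.1) and no turnaround time is given. A check made at the 2-day minimum would not cover ECGs recorded later.
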